### 3.2.2 Secondary Safety Endpoints

The secondary safety endpoints of this study include:

- Treatment-emergent adverse events (TEAEs) and SAEs

- AESI and AEPI (see Section 3.2.3.2) and imAEs (see Section 3.2.3.3)
- ECG
- Vital signs including systolic blood pressure (SBP), diastolic blood pressure (DBP) and pulse rate
- Laboratory data including clinical chemistry, haematology and urinalysis
- Physical examination

### **3.2.3 Adverse Events**

AEs and SAEs will be collected throughout the study, from time of the patient signing the informed consent and 90 days after the last dose of durvalumab. A treatment emergent adverse event (TEAE) is an AE with an onset date or a pre-existing AE worsening following the first dose of study treatment through to 90 days after the last dose of durvalumab.

The Medical Dictionary for Regulatory Activities (MedDRA) (using the latest or current MedDRA version) will be used to code the AEs. AEs will be graded according to the National Cancer Institute Common Terminology Criteria for AEs (CTCAE Version 5.0). The meaning of these categories are as follows:

- Grade 1: Mild AE
- Grade 2: Moderate AE
- Grade 3: Severe AE
- Grade 4: Life-threatening or disabling AE
- Grade 5: Death related to AE

Any TEAE will be included in the AE summaries as detailed in Section 4.5.1.

Missing start and stop dates for AEs will be imputed using the rules described in Section 4.1.3.

#### **3.2.3.1 Possibly-Related Adverse Events**

A PRAE is any TEAE with a relatedness to durvalumab of possible, or where the relatedness is missing. When the relatedness of a TEAE is missing on the electronic Case Report Form (eCRF), all efforts will be taken to ensure that the Investigator assigns his/her assessment of relatedness prior to DBL.

If relatedness of a TEAE is missing at the DBL, as given in Section 4.1.2, the TEAE will be considered as possibly related to durvalumab.

#### **3.2.3.2 Adverse Events of Special Interest and AEs of Possible Interest**

Some clinical concepts (including some selected individual preferred terms and higher-level terms) have been considered “AEs of special interest” (AESI) and “AEs of possible interest” (AEPI) to the durvalumab program.

The AESIs reported in the AstraZeneca-sponsored durvalumab studies are defined as AEs that have a likely inflammatory or immune-mediated pathophysiological basis resulting from the mechanism of action of durvalumab and requiring more frequent monitoring and/or interventions such as corticosteroids, immunosuppressants, and/or endocrine therapy. Endocrine therapies include standard endocrine supplementation, as well as treatment of symptoms resulting from endocrine disorders (for example, therapies for hyperthyroidism include beta blockers [e.g., propranolol], calcium channel blockers [e.g., verapamil, diltiazem], methimazole, propylthiouracil, and sodium perchlorate, infusion-related reactions and hypersensitivity/anaphylactic reactions).

The AEPIs reported in the AstraZeneca-sponsored durvalumab studies are defined as AEs that could have a potential inflammatory or immune-mediated pathophysiological basis resulting from the mechanism of action of durvalumab but are more likely to have occurred due to other pathophysiological mechanisms, thus, the likelihood of the event being inflammatory or immune-mediated in nature is not high and/or is most often or usually explained by the other causes.

These AESIs and AEPIs have been identified as Pneumonitis, Hepatic events, Diarrhea/Colitis, Intestinal perforations, Adrenal Insufficiency, Type 1 diabetes mellitus, Hyperthyroid events, Hypophysitis, Hypothyroid events, Thyroiditis, Renal events, Dermatitis/Rash, Pancreatic events, Myocarditis, Myasthenia gravis, Guillain-Barre syndrome, Myositis, Infusion/hypersensitivity reactions and Other rare/miscellaneous. Other categories may be added or existing terms may be merged as necessary. An AstraZeneca medically qualified expert after consultation with the Global Patient Safety Physician has reviewed the AEs of interest and identified which MedDRA preferred terms contribute to each AESI/AEPI. A further review will take place prior to Database lock (DBL) to ensure any further terms not already included are captured within the categories.

### **3.2.3.3 Immune-Mediated Adverse Event (ImAE)**

An imAE is defined as an AESI that is associated with drug exposure and is consistent with an immune-mediated mechanism of action and where there is no clear alternate etiology. In general, imAEs will include AESIs/AEPI that are managed using steroids, immunosuppressants and/or hormone replacement therapy.

This document comprises the specification for the analysis of the imAEs as identified by the investigator (as recorded in CRF Adverse Events (AE)). No adjudication of the imAEs will be performed for this analysis.

### **3.2.3.4 Confirmed/Suspected COVID-19 infections**

Confirmed/Suspected Covid-19 infection is defined as an AE occurring during the pandemic timeframe (after 11th of March 2020) with preferred term within the AE search criteria developed by the latest MedDRA maintenance and support service organization (MSSO) guidance.

### 3.2.4      **Electrocardiograms**

These measurements are recorded as detailed in the study schedule (See [Appendix A](#)). If vital signs, ECG and blood draws for laboratory tests are scheduled at a visit, they will always be performed in the order: ECG, vital signs and then blood draws.

At Screening, and as clinically indicated throughout the study, ECGs should be obtained after the patient has been in a supine position for 5 minutes and recorded while the patient remains in that position. From these resting 12-lead ECGs values of the QT and RR intervals and the QT interval corrected for heart rate using Fridericia's correction (QTcF) is derived using the following formula:

- $QTcF = QT/RR^{(1/3)}$  where RR is in seconds

In case of clinically significant ECG abnormalities, 2 additional 12-lead ECGs will be performed. All three ECGs should include a value of QTcF over a brief period (eg, 30 minutes). A QTcF value  $>470$  msec will confirm the ECG abnormality finding.

The value of QTcF will be re-derived from the values of RR and QT during the creation of the reporting database.

### 3.2.5      **Vital Signs**

Vital signs measurements will be collected at the start of each treatment cycle as detailed in the schedule of assessment ([Appendix A](#)).

Measurements will include respiration rate (breaths/minute), SBP (mmHg), DBP (mmHg), pulse rate (beats/min), weight (kg), height (cm) and body temperature (degrees Celsius).

### 3.2.6      **Laboratory Data**

Laboratory data (clinical chemistry, haematology and urinalysis) will be collected at the start of each treatment cycle as detailed in the schedule of assessment ([Appendix A](#)). Coagulation will be reported as clinically indicated. Laboratory data will be from local laboratories and will be converted to AZ preferred units, and AZ project reference ranges will be used for the primary interpretation of laboratory data.

The following laboratory parameters will be measured at screening, Day 1 of each cycle, and at other times if clinically indicated:

- Clinical Chemistry: albumin, ALP, ALT, amylase and/or lipase, AST, calcium, glucose, LDH, potassium, sodium, total bilirubin, total protein, TSH, urea or BUN (depending on local practice)
- Haematology: haemoglobin, neutrophil count (absolute or percentage), lymphocyte count (absolute or percentage), platelets, total white cell count
- Urinalysis: bilirubin, blood, color and appearance, glucose, ketones, pH, protein, specific gravity

Corrected calcium product will be derived during creation of the reporting database using the following formula:

$$\text{Corrected calcium (mmol/L)} = \text{Total calcium (mmol/L)} + ([40 - \text{Albumin (g/L)}] \times 0.02)$$

In addition, the following laboratory parameters will be collected at baseline, Day 1 of Cycle 1, or when clinically indicated:

- Clinical Chemistry: bicarbonate (when available), chloride, creatinine clearance, gamma glutamyltransferase, magnesium, T3 free, T4 free
- Haematology: activated partial prothrombin time (ratio or absolute), INR

### **3.2.7 Physical Examination**

Physical examinations will be performed as detailed in the schedule of assessment (Appendix A). Full physical examinations will include assessments of the head, eyes, ears, nose, and throat and the respiratory, cardiovascular, gastrointestinal, urogenital, musculoskeletal, neurological, dermatological, hematologic/lymphatic, and endocrine systems. Height will be measured at screening only. Targeted physical examinations are to be utilized by the Investigator on the basis of clinical observations and symptomatology. Situations in which physical examination results should be reported as AEs are described in Section 8.3.7 of the CSP.

### **3.2.8 Exposure to Durvalumab**

The total (or intended) exposure (weeks) of durvalumab is defined as:

- Total treatment duration (weeks) = Total treatment duration (days) / 7

where:

$$\text{Total treatment duration (days)} = [\text{earliest of (last dose date where dose} > 0\text{mg} + 27 \text{ days, death date, data cut-off date [DCO]-first dose date}]] + 1$$

The actual exposure (weeks) of durvalumab is defined as:

- Actual treatment duration (weeks) = [total treatment duration (days) – total duration of dose delays (days)] / 7.

Dose reductions are not permitted per the CSP for durvalumab and the actual exposure calculation makes no adjustment for any dose reductions that may have occurred.

As patients are scheduled to receive 1500 mg via IV infusion every 4 weeks (28 days), the duration of dose delays is the sum of all individual dose delays as follows:

- Total duration of dose delays (days) = sum of maximum[0, (date of dose [x+1] – date of dose [x] - 28 days)].

If no delays were encountered, the total duration of dose delays would sum up to 0.

According to the protocol, dose delays are defined as doses administered 4 or more days after the target dosing date and reason for dose delay is collected in the CRF based on this definition.

Relative dose intensity (RDI) is the percentage of the actual dose intensity delivered relative to the intended dose intensity through to treatment discontinuation.

RDI is defined as follows:

$RDI = 100\% * d/D$ , where  $d$  and  $D$  are, respectively, the actual and intended cumulative doses delivered up to the date of durvalumab discontinuation or progressive disease or the data cut-off date, whichever occurs earlier.  $D$  is the total dose that would be delivered if there were no modification to dose or schedule.

Percentage intended dose (PID) is the percentage of the actual dose delivered relative to the intended dose through to disease progression.

$PID = 100\% * d_1/D_1$ , where  $d_1$  is the actual cumulative dose delivered up to the earlier of progression (or a censoring event) or the data cut-off date and  $D_1$  is the intended cumulative dose up to the earlier of progression (or a censoring event) or the data cut-off date.  $D_1$  is the total dose that would be delivered, if there were no modifications to dose or schedule.

When deriving actual dose administered the volume before and after infusion will also be considered.

To illustrate the calculation of RDI, [Table 5](#) shows an example of durvalumab dosing for 4 patients.

**Table 5 Example dose intensity scenarios**

RDI	Patient	Study Day									
		1	29	57	85	113	141	169	197	225	230
100%	1	X	X	X	X	X	X	X	X	X	PD
100%	2	X	X	X	X	X	X	X	X[D]		PD
56%	3	X		X		X	O	X	X		PD
67%	4	X	X	O	X	X	X	O	X	O	PD

X: Dose of 1500mg taken; O: Dose missed; [D]: Dose discontinued; PD: Progressive Disease

In this example, all 4 Patients progressed on Day 230, and so the intended dose through to progression was  $9 * 1500\text{mg}$  of durvalumab = 13500mg (13.5g).

Patient 1 received a total of 13.5g of durvalumab, whereas other patients received less durvalumab due to:

- Early stopping prior to PD (Patient 2)
- Dosing delays (Patient 3)
- Missed doses (Patient 4)

For RDI the examples of Patients 2 and 4 illustrate that the end of actual dosing period is calculated based on the smallest recovery period after the last non-zero dose.

Patient 1:  $RD\bar{I} = (9 * 1.5g) / 13.5g = 100\%$

Patient 2:  $RD\bar{I} = (8 * 1.5g) / 12g = 100\%$

Patient 3:  $RD\bar{I} = (5 * 1.5g) / 13.5g = 56\%$

Patient 4:  $RD\bar{I} = (6 * 1.5g) / 13.5g = 67\%$

For the examples the PID differs from RDI for Patient 2 where the calculation is based on the intended cumulative dose up to disease progression regardless of treatment discontinuation.

Patient 1:  $RD\bar{I} = (9 * 1.5g) / 13.5g = 100\%$

Patient 2:  $PDI = (8 * 1.5g) / 13.5g = 89\%$

Patient 3:  $RD\bar{I} = (5 * 1.5g) / 13.5g = 56\%$

Patient 4:  $RD\bar{I} = (6 * 1.5g) / 13.5g = 67\%$

Exposure will also be measured by the number of cycles (doses) of durvalumab received. If a cycle is prolonged due to toxicity this will still be counted as one cycle. A cycle will be counted if treatment is started, even if the full dose is not delivered.

### **3.3 Efficacy Variables**

All RECIST assessments, whether scheduled or unscheduled, and regardless of whether a patient discontinues durvalumab treatment or receives another anti-cancer therapy will be included in the calculation of efficacy variables.

#### **3.3.1 Progression-Free Survival**

Progression-free survival is defined as the time from the date of first dose of durvalumab until the date of objective disease progression or death (by any cause in the absence of progression) regardless of whether the patient discontinues durvalumab or receives another anticancer therapy prior to progression.

- $PFS \text{ (days)} = (\text{date of PFS event or censoring}) - (\text{date of first dose of durvalumab}) + 1$ .

Patients who have not progressed or died at the time of analysis will be censored at the date of their last evaluable tumor assessment (ie, this doesn't include NE or missing value).

If the patient progresses or dies after 2 or more missed visits, the patient will be censored at the date of the latest evaluable assessment prior to the missed visits.

If the patient has no evaluable visits or does not have baseline data, he/she will be censored at Day 1 unless he/she dies within 2 visits of baseline, in which case the date of death is the event date.

Given the scheduled visit assessment scheme (i.e. eight-weekly for the first 48 weeks then twelve-weekly thereafter) the definition of 2 missed visits will change.

1. If the previous RECIST assessment is baseline then two missing visits will equate to 17 weeks since the previous RECIST assessment, allowing for a late visit (i.e.  $2 \times 8$  weeks + 1 week for a late assessment = 17 weeks).
2. If the previous RECIST assessment is post baseline and less than study day 274 (i.e. week 39) then two missing visits will equate to 18 weeks since the previous RECIST assessment, allowing for early and late visits (i.e.  $2 \times 8$  weeks + 1 week for an early assessment + 1 week for a late assessment = 18 weeks).
3. If the two missed visits occur over the period when the scheduled frequency of RECIST assessments changes from eight-weekly to twelve-weekly this will equate to 22 weeks (i.e. take the average of 8 and 12 weeks which gives 10 weeks and then apply same rationale, hence  $2 \times 10$  weeks + 1 week for an early assessment + 1 week for a late assessment = 22 weeks). The time period for the previous RECIST assessment will be from study days 274 to 344 (i.e. week 39 to week 49).
4. From week 49 onwards (when the scheduling changes to twelve-weekly assessments), two missing visits will equate to 26 weeks (i.e.  $2 \times 12$  weeks + 1 week for an early assessment + 1 week for a late assessment = 26 weeks).

If the patient has no evaluable visits or does not have baseline data, he/she will be censored at Day 1 unless he/she dies within 2 visits of baseline, in which case the date of death is the event date.

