- l Tuberculosis testing is to be performed as needed in line with local practice.
- m For women of childbearing potential only. A urine or serum pregnancy test is acceptable. Women of childbearing potential are required to have a pregnancy test within 7 days prior to the first dose of study drug and then every 4 weeks. Pregnancy test may occur on Day 1, but results must be available and reviewed by the treating physician or Investigator prior to commencing an infusion.
- n For AEs/SAEs reported during screening, additional information such as medical history and concomitant medications may be needed.
- o Results for LFTs, electrolytes, and creatinine must be available and reviewed by the treating physician or Investigator before commencing an infusion (within 3 days).

p CCI

q CCI

r CCI

s CCI

t CCI

- u Patients will have baseline scans collected no more than 28 days before the first dose and, ideally, should be performed as close as possible to the first dose. If imaging procedures were performed for alternate reasons prior to signing consent, these can be used for screening purposes with consent of the patient. However, all screening imaging scans must have been obtained within 28 days prior to randomization. RECIST 1.1 assessments will be performed based on local institutional imaging results, using CT/MRI assessments of the chest and abdomen (including the entire liver and both adrenal glands). Additional anatomy

should be imaged based on signs and symptoms of individual patients, including new lesions at follow-up. If an unscheduled assessment was performed and the patient has not progressed, every attempt should be made to perform the subsequent assessments at their scheduled visits (relative to the date of IP treatment initiation). All confirmatory scans should be recorded in the database. For patients who are clinically stable and being treated through radiological progression, the follow-up scan performed after a RECIST 1.1-defined PD should be performed preferably at the next (and no later than the next) scheduled imaging visit, and no less than 4 weeks after the prior assessment of PD. For these patients the assessments should continue as indicated here. Special Confirmation of Radiological Progression criteria apply for tumor assessments on the follow-up scan ([Appendix F](#)).

Note: If a patient has a delay to an infusion of study drug, the efficacy and CCI should be conducted relative to the date of first dose administration.

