### **3. ANALYSIS VARIABLES**

#### **3.1 Derivation of RECIST Visit Responses**

For all patients, the RECIST tumor response data will be used to determine each patient's visit response according to RECIST version 1.1. It will also be used to determine, if and when a patient's disease has progressed in accordance with RECIST and their best objective response to study treatment.

The baseline radiological tumor assessment is part of the screening procedure and should be performed within 28 days after the end of radiotherapy, no more than 28 days before the start of durvalumab treatment, and ideally as close as possible to the start of study treatment. Tumor assessments will begin at 8 weeks  $\pm$  1 week after durvalumab initiation and continue every 8 weeks  $\pm$  1 week through 48 weeks (relative to the date of first dose of durvalumab), and then every 12 weeks  $\pm$  1 week thereafter until RECIST 1.1-defined PD, plus an additional regularly scheduled follow-up scan. The on-study schedule of q8w  $\pm$  1 week (following the first assessment at 8 weeks  $\pm$  1w after the first dose) for first 48 weeks and then q12w  $\pm$  1 w thereafter MUST be followed regardless of any delays in dosing. Additional scans can be completed per standard practice post disease progression.

From the investigator's review of the imaging scans, the RECIST tumor response data will be used to determine each patient's visit response according to RECIST version 1.1. At each visit, patients will be programmatically assigned a RECIST 1.1 visit response of CR, PR, SD or PD, using the information from target lesions (TLs), non-target lesions (NTLs) and new lesions and depending on the status of their disease compared with baseline and previous assessments. If a patient has had a tumor assessment which cannot be evaluated, then the patient will be assigned a visit response of not evaluable (NE) (unless there is evidence of progression in which case the response will be assigned as PD).

RECIST outcomes (ie, PFS and ORR etc.) will be calculated programmatically from site investigator data from overall visit responses.

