- The data will be included in summaries/analyses using the following criteria:
  - All laboratory data, vital signs and ECG data that are recorded at unscheduled visits will be included in the summaries using the visit windows defined in Section 4.1.4.1.
  - The tumor measurements and PRO data should not be affected by any delays in treatment cycles/dates of start of treatment cycles as it is intended that they are only recorded at pre-scheduled time points. These data will be included in the summaries and analyses of the data using the visit windows defined in Section 4.1.4.2.
- All data collected including scheduled, delayed and unscheduled data will be listed in the patient data listings which are produced for all treated patients. They will be ordered by treatment/not treated, centre, radiotherapy group, patient and visit and, if relevant, timepoint when they were recorded. Patients who are included in the SAF will be flagged. Depending on the availability of the data, all data for the patients who are not treated will be listed separately. They will be ordered by centre, radiotherapy group, patient and visit and timepoint, if relevant.
- All adverse events will be coded using MedDRA and NCI CTCAE Grade and will be reported using SOC and PT, and NCI CTCAE Grade, as appropriate.
- All concomitant and previous medications will be coded using WHO drug dictionary and will be reported using anatomical therapeutic chemical (ATC) classification and generic term.
- Baseline is defined as the last assessment of the variable under consideration prior to the first dose of durvalumab regardless of whether the assessment is on Day 1, Screening or unscheduled.
- Patients who failed the screening in the first instance but later rescreened and passed the screening will be part of summary tables along with other patients who passed the screening in the first instance.
- Patients who failed both first screening and rescreening will not be part of summary tables but a listing will be generated for these patients.

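### Rule 1 for missed visits in SAP 3.3.1 counts its 17 weeks from the baseline scan, not first dose, so one missed scan can be treated as two and an early PFS event dropped

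*SAP*

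**What the plan says.** SAP 3.3.1 discards a PFS event that follows a long gap in tumour assessment. The parent rule counts visits: "If the patient progresses or dies after 2 or more missed visits", the patient is "censored at the date of the latest evaluable assessment prior to the missed visits". Protocol 9.4 has the same rule, also in visits and without a week count.

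SAP 3.3.1 then converts two missed visits into weeks by four rules. Rule 1 covers a patient whose last assessment was baseline: "If the previous RECIST assessment is baseline then two missing visits will equate to 17 weeks since the previous RECIST assessment". Its sum is two 8-week intervals plus "1 week for a late assessment = 17 weeks".

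The baseline scan precedes treatment. SAP 3.1 requires it "no more than 28 days before the start of durvalumab treatment", and footnote u to Table 1 in protocol 1.1 agrees: "Patients will have baseline scans collected no more than 28 days before the first dose". SAP 4.1.1 does not move that date to Day 1: "Baseline is defined as the last assessment of the variable under consideration prior to the first dose of durvalumab". On-study scans are timed from first dose (protocol 1.1, SAP 3.1): every 8 weeks ± 1 week through Week 48.

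A separate clause of SAP 3.3.1 names Day 1 as a censoring date: "If the patient has no evaluable visits or does not have baseline data, he/she will be censored at Day 1". Its exception keeps a death as an event if it occurs within two visits of baseline.

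**The concern.** The length of the rule 1 limit and its starting point do not belong together. Seventeen weeks is right for a clock that starts at first dose. The sentence starts the clock at the baseline scan, which can be four weeks earlier, and allows nothing for that gap. A patient who missed one scan can therefore exceed a limit meant to identify two missed scans. That contradicts the parent rule in the same section and protocol 9.4.

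The events at risk are early ones: progressions first seen at Week 16 in patients without a Week 8 scan and, on one reading, early deaths. Removing them and censoring near time zero raises the early Kaplan-Meier curve and PFS6. Whether such an event counts would depend on how early the screening scan was done, not on how many visits were missed.

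**Working it through.** **1. The plan's own figures.** Rule 1: 2 × 8 + 1 = 17 weeks = 119 days. Rule 2: 2 × 8 + 1 + 1 = 18. Rule 3: 2 × 10 + 1 + 1 = 22. Rule 4: 2 × 12 + 1 + 1 = 26. All reproduce. Rules 2 to 4 add a week because the previous scan may have been early, and a week because the next may be late. Rule 1 adds only the late week. That fits a fixed origin at first dose, from which the Week 16 window runs 105 to 119 days.

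**2. Elapsed time under the wording.** Let k be the number of days from baseline scan to first dose (up to 28). A scan d days after first dose is d + k days after the baseline scan. Rule 1 drops the event if d + k > 119.

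| Week 16 visit scanned at | d | Dropped when | Elapsed at k = 28 |
|---|---|---|---|
| Week 15 (earliest) | 105 | k > 14 | 133 days = 19.0 weeks |
| Week 16 (Day 113) | 112 | k > 7 | 140 days = 20.0 weeks |
| Week 17 (latest) | 119 | k ≥ 1 | 147 days = 21.0 weeks |

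A Week 8 scan is never affected: at most 63 + 28 = 91 days.

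**3. Are gaps above 7 days plausible?** SAP 3.1 asks for the baseline scan within 28 days after the end of radiotherapy. Inclusion criterion 7 allows first dose up to 42 days after it. A patient dosed 36 to 42 days after radiotherapy whose scan meets SAP 3.1 has a gap of at least 36 − 28 = 8 to 42 − 28 = 14 days. Neither document gives a distribution of gaps.

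**4. Recorded PFS.** PFS is the event or censoring date minus the first-dose date, plus 1. An event on Day 113 gives 113 days. Censoring at a baseline scan 28 days before first dose gives −28 + 1 = −27 days, and a 1-day gap gives 0. Censoring at Day 1 gives 1 day.

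**5. Deaths, if the exception uses the same 17 weeks.** With no post-baseline scan, the last death counted falls on Day 119 − k + 1. That is Day 120 at k = 0 and Day 92 at k = 28.

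**6. Size, under assumptions.** The documents give no missed-scan rate. Assume 102 patients, k uniform over 1 to 28 days, exponential PFS with median 6 or 12 months (182.5 or 365 days), 15% or 5% missing Week 8, and progression seen at nominal scan days. The share of gaps that drop a Day 113 event is 21/28 = 75%.

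- 6-month median, 15% missing. Event by Week 16: 1 − 0.5^(112/182.5) = 0.346. Events lost: 102 × 0.15 × 0.346 × 0.75 ≈ 4.0. PFS6 with events counted through the Week 24 scan: 0.5^(168/182.5) = 0.528. With the lost patients out of the risk set: 0.528 × 102/(102 − 4.0) = 0.550, or about 2 points higher.
- 12-month median, 5% missing. Event by Week 16: 1 − 0.5^(112/365) = 0.192. Events lost: 102 × 0.05 × 0.192 × 0.75 ≈ 0.7. PFS6: 0.5^(168/365) = 0.727, against 0.727 × 102/(102 − 0.7) = 0.732, or about 0.5 points higher.

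Simulations over the same ranges give about 0.6 to 4 events lost and about 0.4 to 2 points on PFS6. For scale, a 95% half-width for a proportion near 50% with n = 102 is 1.96 × √(0.25/102) ≈ 9.7 points.

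**The case against.** The strongest reply is that the intended origin is plain. The parent rule counts missed visits, visits are fixed from first dose, and SAP 4.1.4.2 assigns each scan to its scheduled or nearest visit. On that count a patient scanned at Week 16 after missing Week 8 has missed one visit and keeps the event. The missing early week in rule 1 also suggests that baseline was being treated as Day 1. This stands as evidence of intent. It does not rescue the text: rule 1 is the operational definition, it names the previous assessment as its origin, and no section overrides it. A programmer following it gets the wrong result.

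Other replies limit the point, and stronger readings that a reader might infer do not hold:

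- That the 17-week sum is wrong. It is correct; only its starting point is wrong.
- That the SAP expressly censors these patients at Day 1. The Day 1 clause covers patients with no evaluable visits or no baseline data, and a patient with evaluable progression at Week 16 is neither. The literal censoring date is the baseline scan; Day 1 is the practical result.
- That early deaths are certainly lost. The SAP does not tie the death exception to the 17 weeks, so this is conditional.
- That every on-time Week 16 progression is dropped, or always 75% of them. The 7-day threshold and 21 of 28 apply to Day 113 only; at Week 15 it is 14 of 28, and at Week 17 it is 28 of 28.
- That the patients affected are the sickest. The documents give no reasons for missing Week 8.

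Both documents also ask for the baseline scan as close as possible to first dose, so a uniform gap may overstate the effect. Unscheduled scans count (SAP 3.3) and could catch some progressions before Week 16.

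**Conclusion.** The concern holds as an error in the rule as written, not as missing detail. Rule 1 pairs a limit built from first dose with a clock started at the baseline scan, and can class one missed visit as two. At a 28-day gap it does so anywhere in the Week 16 window. The literal censoring date then gives PFS of zero or less, which is a second gap in the same rule.

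The bias runs one way, raising PFS6 and the early curve, but it is modest and small beside the sampling error. Its size rests on the assumed gap distribution, missed-scan rate and median PFS; no figure is offered here for median PFS or PFS12. A reader might infer that the trial's main conclusion is at risk. It is not: PFS is secondary and descriptive, and the primary safety endpoint does not use this rule. OS is also unaffected. DoR is defined only for confirmed responders, and a patient with no scan between baseline and progression cannot be one. This is a should-fix.

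**What to change.** Make three changes in SAP 3.3.1.

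1. In rule 1, count the 17 weeks from the date of first dose (Day 1) instead of from the baseline scan. Two missed visits from baseline then means progression or death after Day 120 with no evaluable post-baseline scan before it.
2. Use the same first-dose clock for the exception that covers death within two visits of baseline.
3. State that patients censored under rule 1 are censored at Day 1.

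Check: with the limit at 119 days from first dose, Week 16 scans (105 to 119 days) are never dropped, and Week 24 scans (161 to 175 days) always are after two misses. Keeping the baseline-scan clock and raising the limit to 17 + 4 = 21 weeks (147 days) would also work, since the latest Week 16 case is 119 + 28 = 147 days and the earliest Week 24 case is 161. The first-dose clock is simpler and matches the scan schedule.

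The cost is a few sentences in the SAP and a small programming change, made before the PFS analysis. Data collection and trial conduct do not change.
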